3. INTERIM ANALYSIS AND DATA MONITORING COMMITTEE REVIEW

The IDMC will review the safety data initially after approximately 12 subjects have completed treatment and when approximately 12 Japanese subjects have completed treatment to assess that treatment may safely continue in each arm. A separate SAP will be written that provides details on the data package for this purpose. Details on operational characteristics will be provided in the IDMC Charter.

In addition, a maximum of 2 interim analyses are planned to assess the primary endpoint for early superiority and futility. The first interim analysis will be performed when at least 45 subjects have been randomized, preferably after the end of a hemispheric RSV season. Up to the final database lock, the study team will remain blinded to the results. Details on operational characteristics will be provided in the interim analysis charter. An Interim Analysis SAP will be written that describes this formal interim analysis, focusing on the rules of futility, early superiority and sample size recalculation.

This interim analysis will be based on the subjects randomized up to that timepoint in the ITT-i Set.

The following situations will be considered based on the results of the primary analysis at this stage: that the study is considered futile; that superiority can be concluded (based on an O'Brien-Fleming alpha spending function); that the study is considered underpowered; or that the study should continue unchanged. In the case of the (unbinding) futility boundary or the superiority boundary being crossed, the IDMC will recommend early termination to the Sponsor Committee. If the study is considered underpowered, a sample size increase may be suggested to a maximum of 180 subjects. This blinded sample size calculation will take the residual error variance into account of the primary analysis model.

If early superiority on the primary endpoint can be established, the study may, however, be continued in order to accumulate data to allow the selection of the dose regimen or further substantiate the benefit-risk profile in this population; in this case the randomization ratio of active to placebo treatment may be altered for example, if dose selection is evident from the dose-response analysis, subjects randomized to active treatment may all receive the optimal dose. However, at the interim analyses or at any time, upon recommendation by the IDMC, a dose regimen may be removed or adjusted based on PK, safety, and/or antiviral activity considerations.

The Interim Analysis Committee will be responsible for performing the formal interim analysis and will consist of sponsor personnel who are not otherwise involved in the study. The IDMC will review the data and make recommendations to the Sponsor Committee.

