10.2 Discontinuation of Study Treatment/Withdrawal From the Study

11 STATISTICAL METHODS

Rationale: The following changes were made upon health authority request:

- Addition of a mandatory safety sample for hematology and biochemistry on the Day 28 follow-up visit, to ensure a comprehensive safety evaluation in all subjects.
 - Addition of a follow-up visit 2 days after the last treatment dose for subjects who discontinued treatment early, to be consistent with the Day 7 follow-up visit planned for subjects who completed treatment.
 - Adjustment of the inclusion criteria, exclusion criteria, and potential risk sections to be consistent with recommendations related to contraception and pregnancy testing in clinical trials as described in the Clinical Trial Facilitation Group (CTFG) guidance.⁸
 - o Extension of the duration of contraception (ie, from 90 to 104 days for men and their female partners of childbearing potential, and from 30 to 44 days for heterosexually active women of childbearing potential).
 - o Adjustment of the duration in which female participants are not allowed to donate eggs (ova, oocytes).
 - o Clarification of the contraceptive methods recommended for female partners (if of childbearing potential) of male participants.
 - Given that prescription medications such as palivizumab, ribavirin, and intravenous immunoglobulin used to prevent or treat RSV infection have a half-life that goes beyond 3 days, they have been included in the list of disallowed concomitant medications as prohibited 30 days or 5 half-lives (whichever is longer) before the planned first dose of study drug. Furthermore, it was clarified that prescription medications intended to treat the symptoms/sequelae of the RSV infection are permitted.
 - Adjustment of the definition of the intent-to-treat (ITT) infected population.
 - Clarification that the key findings of the popPK and PK/pharmacodynamic (PD) analysis of this study will be presented in the final clinical study report.
 - Clarification that the interim analysis will be performed upon treatment completion (rather than randomization) by 45 subjects to ensure that adequate data is available for interim analysis review.
-

SYNOPSIS

TIME AND EVENTS SCHEDULE

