3.2. Study Design Rationale

Blinding, Control, Stratification, and Treatment Regimens

There is no approved treatment routinely used for the treatment of RSV infection. A placebo control will be used for both parts of the study to establish the frequency and magnitude of

changes in virologic and clinical endpoints that may occur in the absence of active treatment. The use of a placebo control will allow for any AEs or laboratory abnormalities observed during the course of the study to be evaluated properly, ie, to be able to differentiate between events potentially related to the use of ALS-008176 versus those related to the underlying disease.

Randomization will be used to minimize bias in the assignment of subjects to treatment regimens, to increase the likelihood that known and unknown subject attributes (eg, demographic and baseline characteristics) are evenly balanced across treatment regimens, and to enhance the validity of statistical comparisons across treatment regimens. In Part 1, subjects will be randomized in a 1:2 ratio to receive placebo or the low-dose ALS-008176 dosing regimen. In Part 2, subjects will be randomized in a 1:1:1 ratio to receive 1 of the ALS-008176 regimens or matching placebo. For Part 1, randomization will be stratified by region (Japan versus non-Japan). For Part 2, randomization will be stratified by region (Japan versus non-Japan) and age (≥ 18 to < 65 years and ≥ 65 years). Blinded treatment will be used to reduce potential bias during data collection and evaluation of clinical endpoints.

The number of subjects exposed as part of the study has been limited to the absolute minimum to reach the objectives of the study. For Part 2, the IDMC will be empowered such that if early superiority on the primary endpoint is established, the randomization ratio to placebo may be altered, thereby avoiding unnecessary risk and discomfort to placebo-treated subjects.

Doses Selected

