11.11. Interim Analysis

For Part 2, a maximum of 2 formal interim analyses are planned to assess the primary endpoint for early superiority and futility. The first formal interim analysis will be performed when at least 45 subjects have completed treatment to ensure that adequate data is available for interim analysis review, preferably after the end of a hemispheric RSV season. Up to the final database lock, the study team will remain blinded to the results. Details on operational characteristics will be provided in the interim analysis charter.

The following situations will be considered based on the results of the analysis of the primary endpoint at this stage: that the study is considered futile; that superiority can be concluded (based on an O'Brien-Fleming alpha spending function); that the study is considered underpowered; or that the study should continue unchanged. In the case of the (unbinding) futility boundary being crossed, the IDMC will recommend early termination to the Sponsor Committee. If the study is considered underpowered, a sample size increase may be suggested to a maximum of 180 subjects. This blinded sample size calculation will take the residual error variance into account of the primary analysis model.

If early superiority on the primary endpoint can be established, the study may, however, be continued in order to accumulate data to allow the selection of the dose regimen or further substantiate the benefit-risk profile in this population; in this case the randomization ratio of active to placebo treatment may be altered for example, if dose selection is evident from the dose-response analysis, subjects randomized to active treatment may all receive the optimal dose. However, at the interim analyses or at any time, upon recommendation by the IDMC, a dose regimen may be removed or adjusted based on PK, safety, and/or antiviral activity considerations.

The Interim Analysis Committee will be responsible for performing the formal interim analysis and will consist of sponsor personnel who are not otherwise involved in the study. The IDMC will review the data and make recommendations to the Sponsor Committee.

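### SAP Sections 1.2 and 3 are not aligned with protocol Section 11.11 on when the first interim runs, who is in it, and what follows if the superiority boundary is crossed

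*SAP*

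**What the plan says.** **Trigger and data set.** SAP Section 3 says "The first interim analysis will be performed when at least 45 subjects have been randomized, preferably after the end of a hemispheric RSV season", and Section 1.2 gives the same trigger. Section 3 adds that the analysis uses the ITT-infected (ITT-i) subjects randomized by that point. Protocol Section 11.11 says "The first formal interim analysis will be performed when at least 45 subjects have completed treatment to ensure that adequate data is available" for the review, and the protocol synopsis gives the same trigger.

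**Action at a boundary.** SAP Section 3: "In the case of the (unbinding) futility boundary or the superiority boundary being crossed, the IDMC will recommend early termination to the Sponsor Committee". Protocol Section 11.11: "In the case of the (unbinding) futility boundary being crossed, the IDMC will recommend early termination to the Sponsor Committee". After early superiority, both documents allow the study to go on, to help choose the dose or strengthen the benefit-risk evidence, with a possible change in allocation. Protocol Section 3.2 adds that "if early superiority on the primary endpoint is established, the randomization ratio to placebo may be altered".

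**Information fraction.** SAP Section 4.2.3.2 sets the interim significance level from t' = n/N, where n is the size of the ITT-i set and N is 90.

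**The concern.** These rules settle when the first unblinded look happens, whose data are in it, and what the IDMC is expected to say afterwards. If two governing documents differ, the difference may surface only once someone has seen unblinded results, when either choice can look driven by the data.

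On the trigger, the primary endpoint is the viral load AUC from baseline to Day 7. A subject randomized just before the cut-off may have only one or two swabs. The SAP nevertheless counts that subject as a full unit of information. The protocol gives data adequacy as its reason for waiting until treatment is complete.

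On the action, the SAP makes a recommendation to stop the default response to a superiority crossing. The protocol sets no such default.

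**Working it through.** **1. The texts side by side**

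| Item | SAP 1.2 and 3 | Protocol 11.11 |
|---|---|---|
| First look | at least 45 randomized | at least 45 completed treatment |
| Subjects analysed | ITT-i subjects randomized by then | not spelled out; the trigger is meant to secure adequate data |
| Termination recommendation | futility or superiority | futility only |
| After superiority | may continue (next paragraph) | may continue |

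Protocol Section 10.1 defines completion of the treatment phase as the full regimen plus the Day 7 visit. If the trigger in Section 11.11 is read that way, it secures the whole primary-endpoint window. The SAP trigger does not. As background only, the Amendment 2 rationale records the origin of the protocol rule: "Clarification that the interim analysis will be performed upon treatment completion (rather than randomization) by 45 subjects". The SAP also keeps an age limit of 50 years where the protocol has 18, and it has no Part 1. This fits a SAP that was not updated to the current protocol.

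**2. Effect of the trigger on first-look spending**

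Inputs: one-sided alpha 0.025 (SAP 4.2.1.1), N = 90 and the spending function (SAP 4.2.3.2), and 45 subjects at the first look. The number still incomplete is assumed.

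Formula: spend(t') = 2 − 2Φ(z/√t'), with z = Φ⁻¹(1 − 0.0125) = 2.2414.

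| Incomplete among 45 (assumed) | Completers/90 | Spend at that fraction |
|---|---|---|
| 0 | 45/90 = 0.500 | 0.00153 |
| 5 | 40/90 = 0.444 | 0.00077 |
| 10 | 35/90 = 0.389 | 0.00033 |

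Under the SAP's headcount rule, t' stays at 0.500 and the spend at 0.00153 in every row. The largest gap is 0.00153 − 0.00033 = 0.0012, out of a total of 0.025. The last column is a lower bound on what the available information would justify. SAP 4.2.3.1 and 4.2.3.2 fit a mixed model under missing at random, so the swabs that incomplete subjects do have still contribute.

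**3. Is a superiority crossing at the first look realistic?**

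The plan's stated power was reproduced first. A simulation of the larger of the plateau and linear contrasts used 30 per arm, three looks, the SAP spending function and equal effects in both active arms. It gives 90.6% to 90.8% at d = 0.77 (stated: about 90%) and 81.2% to 81.5% at d = 0.67 (stated: about 80%). With known variance and the first look at 45 of 90, the chance of crossing the superiority bound there (about z = 3.11) is:

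| Dose-response shape | d = 0.77 | d = 0.67 |
|---|---|---|
| Equal effect in both active arms | 27% | 18% |
| Low dose at half the effect | 18% | 12% |

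The superiority rule therefore has a real chance of being used.

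**The case against.** The strongest reply is that this SAP does not govern the interim. Section 2.4 limits it to the final analysis, and Section 3 leaves the rules for futility, superiority and sample size to an interim SAP and a charter. SAP Section 1 says it is to be read together with the protocol. This stands and limits the practical effect. It does not remove an explicit trigger, data set and action that differ from the protocol.

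Several stronger readings are tempting, and the documents do not support them:

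- **An antiviral win would end the trial.** The SAP's next paragraph qualifies the termination sentence by allowing continuation. Under protocol Section 11.12 the IDMC recommends and the Sponsor Committee decides on the action. A default with an exception is coherent, even though it is not the protocol's rule.
- **The protocol forbids stopping for superiority, or requires continuing.** It does neither. It lists superiority as a possible conclusion and only permits continuation.
- **Thin safety data on the high dose measure the discrepancy.** About 15 subjects would be on Regimen C at 45 subjects. With no events, the one-sided 95% upper bound is 1 − 0.05^(1/15) = 18.1%, against 1 − 0.05^(1/30) = 9.5% with 30. The first figure is the same under the protocol trigger, so it says nothing about the difference between the documents. IDMC safety review also runs separately.
- **Type I error is inflated.** No total inflation has been shown. The number in flight is assumed, and both documents prefer a look after a hemispheric season, when few subjects may still be on treatment.

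**Conclusion.** The two interim rules differ between the current SAP and the current protocol and need to be reconciled.

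The trigger difference is the clearer one: the SAP can admit subjects without complete Day 7 swabs and count them fully in n/N. Its numerical effect is bounded. With 5 to 10 of 45 incomplete, the first-look spend is 0.0015, against a lower bound of 0.0003 to 0.0008. That range rests wholly on the assumed number in flight.

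The action difference is one of default. The SAP leans towards a stop recommendation on superiority and then allows continuation. The protocol attaches the recommendation to futility only. The 12% to 27% chance of a first-look crossing depends on the plan's own effect sizes, the dose-response shape and known variance.

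This ranks below a must-fix point, because the interim SAP and charter are the operative documents and could not be seen. It should still be settled before any unblinded look.

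**What to change.** 1. In SAP Sections 1.2 and 3, replace "The first interim analysis will be performed when at least 45 subjects have been randomized" with the protocol rule: "The first formal interim analysis will be performed when at least 45 subjects have completed treatment".
2. In SAP Section 3, base the interim set, and the n used in t' = n/N, on the ITT-i subjects who meet that trigger. The interim SAP should also say how subjects who stop study drug early are counted, since protocol Section 11.11 does not.
3. In SAP Section 3, remove the superiority boundary from the termination sentence so that it matches protocol Section 11.11. Keep the following paragraph that permits continuation, and add no mandatory recommendation to continue, because the protocol contains none.
4. Carry the same wording into the interim SAP and the IDMC charter before any unblinded look.

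The cost is wording only. Sample size, planned power and total alpha do not change. The first look comes about a week later than under the SAP trigger.

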4. ANALYSES

4.1. SUBJECT INFORMATION

All general analyses will be done on the ITT-i Set and the Safety Set, unless specified otherwise for a specific display.

4.1.1. Demographics and Baseline Characteristics

All demographics and baseline characteristics will be summarized overall and by treatment group. Descriptive statistics or frequency tabulation will be provided for the following parameters.

Demographic parameters:

Sex (Male, Female, Undifferentiated)

Race (White, Black or African American, Asian, American Indian or Alaska Native, Native Hawaiian or Other Pacific Islander, Other). The specification of the category ‘Other’ will only be listed.

Ethnicity (Hispanic or Latino, Not Hispanic or Latino)

Country (from [DM] dataset)

Geographic region (based on country: North America [to include Puerto Rico], Europe, South America, Asia-Pacific)

Age (years)

Weight at baseline (kg)

Height at baseline (cm)

BMI at baseline = Weight at baseline (kg) / (Height at baseline (m))²

(rounded to 1 decimal. Even if available in the raw data, BMI will be recalculated from baseline weight and height)

Baseline disease characteristics:

Duration of RSV symptoms prior to first treatment (days)

Presence of comorbidities (yes, no)

Comorbid diseases associated with risk for lower respiratory tract disease^{[1][2]} (yes, no) and proportion of subjects suffering from each of the following diseases:

- Asthma
- COPD
- CHF
- CAD (coronary artery disease)

Other conditions/therapy of potential interest due to risk of infections in general (yes, no) and proportion of subjects with each of the following conditions/therapies:

- Diabetes mellitus
- CRF (Chronic Renal Failure)
- Use of systemic corticosteroids (PO, IV) prior to or during the treatment

Baseline RSV Viral load (log₁₀ copies/mL)

Previous use of aerosolized ribavirin (yes, no)

Previous use of IV immunoglobulin (yes, no)

Oxygen Saturation (%)

Receiving Supplemental Oxygen (yes, no)

Intravenous or enteral tube feeding (yes, no)

Intravenous or enteral tube hydration (yes, no)

Respiratory Rate (breaths/min)

Heart Rate (beats/min)

4.1.2. Disposition Information

Summaries will be provided for the following disposition information:

- Number of subjects screened, screen failures, randomized or treated, not randomized, randomized and not treated, treated and not randomized, safety set, randomized and treated, treated but not RSV infected, treated and RSV infected and per protocol set.
- Number of subjects who completed or discontinued treatment and the trial, with a breakdown of the reasons of discontinuation.
- Number of subjects per phase and per visit in the trial.

4.1.3. Treatment Compliance

Dosing compliance is calculated as the actual number of doses taken, as a percentage of the planned number of doses. The actual number of doses can be calculated from the number of doses dispensed (18 tablets) minus the number of doses returned (from [da] data set: number of tablets returned). The planned number of tablets is 12. In case the length of duration is increased, the calculation will take the new planned number into account.

Dosing compliance will be summarized descriptively by treatment group.

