6. DOSAGE AND ADMINISTRATION

The study drug ALS-008176 will be provided as tablets for oral administration. Study drug administration should start as soon as possible, but no later than 4 hours after randomization in

order to maximize the opportunity for the compound to inhibit viral replication and potentially improve outcomes.

Subjects will be dosed with a single LD followed by 9 MDs twice daily (at least 8 hours apart and maximum 16 hours apart, with no more than 2 doses per calendar day) during Day 1 to Day 5/6 (depending on the timing of the LD administration). In Part 1, subjects will be randomized in a 1:2 ratio to Regimen A or B. In Part 2, subjects will be randomized in a 1:1:1 ratio to Regimen A, B, or C.

	Regimen A^a	Regimen B^a	Regimen C^a
Treatment Regimen	Placebo	Low-dose ALS-008176: 750 mg LD/250 mg MD	High-dose ALS-008176: 1,000 mg LD/500 mg MD
Loading Dose	Placebo: 1 intake of 3 tablets	ALS-008176: 1 intake of 3 x 250 mg tablet	ALS-008176: 1 intake of 2 x 500 mg tablet Placebo: 1 intake of 1 tablet
Maintenance Dose	Placebo: 9 intakes of 1 tablet	ALS-008176: 9 intakes of 1 x 250 mg tablet	ALS-008176: 9 intakes of 1 x 500 mg tablet

^a Placebo tablets will be visually identical to their active drug counterparts.

Administration of each dose should occur at approximately the same time each day. ALS-008176 can be administered without regard to food intake. The date and time of dose administration, the date and time of food intake (limited to the food ingested within 30 minutes before or after study drug administration), and the type of food will be recorded in the eCRF during hospitalization.

In case the subject is discharged prior to the completion of dosing, study drug administration will be continued at home until all doses are administered (Day 5/6), and the date and time of dose administration will be recorded in the electronic device used for eCOA. The investigator/study-site personnel will instruct subjects on how to store the study drug for at-home use as indicated for this protocol.

An overdose in this study is defined as a calculated dose exceeding the planned dose.

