Study drug administration continues until 10 doses have been taken. Subjects will receive 9 MDs without regard to food intake twice daily (at least 8 hours apart and maximum 16 hours apart, with no more than 2 doses per calendar day) through Day 5/6 (depending on the timing of the LD administration). The date and time of dose administration, the date and time of food intake (limited to the food ingested within 30 minutes before or after study drug administration), and the type of food will be recorded in the eCRF during hospitalization. The subject may be discharged after Day 2 following completion of study procedures. Subjects may also remain hospitalized if warranted by the subject's clinical status. In case the subject is discharged prior to the completion of treatment, study drug will continue to be administered at home by the subject until all doses are administered (Day 5/6), and the date and time of dose administration will be recorded in the electronic device used for eCOA. Instructions will be given to the subject regarding drug administration by the investigator or a qualified member of the study-site personnel.

Assessments will be performed as detailed in the [Time and Events Schedule](#). The eCOA (investigator and subject questionnaires) and the mid-turbinate nasal swabs (if non-intubated) (from the same nostril throughout the study) or the mid-turbinate nasal swab and endotracheal samples (if intubated) are to be taken once daily prior to study drug administration at approximately the same time each day (see [Figure 3](#)). In case of nostril bleeding or irritation during the collection of a mid-turbinate nasal swab, all subsequent nasal swabs will be performed on the contralateral nostril. Samples will be collected through Day 6 whether the subject is in hospital or has been discharged. Should the study drug duration be increased to up to 10 days (following review of the data by the IDMC), samples will be taken every day up to and including 1 day (+2 days) following the last dose of study drug. In case mid-turbinate nasal swabs are

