2.3. Analysis sets

The analysis populations covered by this SAP will be:

Randomized Analysis set (RAND): All randomized subjects with a randomization date at or before the date of first intake of medication, or with a randomization date and a missing date for first medication intake.

Safety Set or All Subjects Treated set (AST): All subjects who received at least 1 dose of study drug, analyzed as treated.

Randomized or Treated (RT) set: All subjects who are in the Randomized Analysis Set (RAND) and/or the All Subjects Treated (AST) set.

Intention-To-Treat (ITT) set: All randomized subjects who receive at least 1 dose of study drug. Analyses on the ITT Set will be analyzed as randomized.

Intention-To-Treat-infected (ITT-i) set: All randomly assigned subjects who receive at least 1 dose of study drug and who have an RSV infection confirmed by a PCR-based assay at the central laboratory.

For the interim analysis: a subject is considered to have a confirmed infection with RSV if he/she has been diagnosed with RSV infection based on a PCR-based assay at the local laboratory and for which the RSV infection is confirmed by central laboratory or for which the result of the central laboratory testing is not available at cut-off.

Analyses on the ITT-i Set will be analyzed as randomized.

Per-Protocol (PP) Analysis set: All subjects in the ITT-i set who do not have protocol violations that may have an impact on the efficacy analysis. Decisions regarding which subjects are included in the PP set will be made before database lock on following criteria:

- Compliance: Subjects must have at most 1 missed dose. On the day of randomization at least one dose needs to be taken (so missed dose cannot be the first dose).
- The actual treatment must be the same as the planned treatment.
- No unblinding may have taken place during the study.
- Subjects will be excluded from the PP set if they have taken concomitant medications that may have affected the efficacy of the trial medication. Subjects will be excluded on a case by case basis using a list provided by clinical.
- Subjects may not violate inclusion criteria 3 or 4, nor exclusion criteria 1, 3, 8, 9, 10 or 13.

Analyses on the Per-Protocol set will be analyzed as randomized. Note that in the Per-Protocol set subjects will have been treated as randomized by definition.

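### SAP 4.1.3 defines compliance in doses but computes it from tablets, and the first-dose rule for the per-protocol set in SAP 2.3 does not match the protocol's 4-hour limit

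*SAP*

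**What the plan says.** **Compliance (SAP 4.1.3).** The definition is in doses: "Dosing compliance is calculated as the actual number of doses taken, as a percentage of the planned number of doses". The derivation is in tablets: "The actual number of doses can be calculated from the number of doses dispensed (18 tablets) minus the number of doses returned", with the returned figure taken as a number of tablets. The planned figure is also in tablets: "The planned number of tablets is 12". If dosing is lengthened, the SAP says the calculation will use the new planned number; it does not mention the number dispensed. The result is summarized descriptively by arm.

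**Regimen (Protocol 6 and 9.1.3).** "Study drug administration continues until 10 doses have been taken". For Regimen B the loading dose is "1 intake of 3 x 250 mg tablet" and maintenance is "9 intakes of 1 x 250 mg tablet". The other arms have the same tablet counts; in Regimen C one of the three loading tablets is placebo.

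**Dose records.** In hospital, the date and time of each dose go into the eCRF. After discharge, "the date and time of dose administration will be recorded in the electronic device used for eCOA" (Protocol 6). Protocol 7 also requires a site log of study drug administered.

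**Per-protocol set (SAP 2.3).** At most one dose may be missed, with no data source named. In addition, "On the day of randomization at least one dose needs to be taken", which the SAP explains as ensuring that the missed dose is not the first one. Protocol 6 and 9.1.3 set a different limit: the first dose no later than 4 hours after randomization.

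**The concern.** A compliance measure is useful for subjects who did not take everything. Here the stated unit (doses) and the computed unit (tablets) differ for exactly those subjects, because one dose is worth three tablets and the other nine are worth one each. Missing the loading dose and missing three maintenance doses get the same score. Dispensing more tablets than planned also makes the result depend on what comes back.

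The per-protocol rule is a separate matter. It replaces an elapsed-time limit with a same-day condition, and the two can disagree in both directions. At stake is whether the per-protocol set, which supports the primary and selected secondary endpoints, consists of subjects treated within the protocol's own timing limit.

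**Working it through.** **Inputs.** Loading dose: 3 tablets. Maintenance: 9 doses of 1 tablet (Protocol 6). Dispensed: 18 tablets. Planned: 12 tablets (SAP 4.1.3).

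**Reproducing the plan's figure.** Tablets: 3 + 9 = 12, which agrees with the SAP. Doses: 1 + 9 = 10. Expected returns: 18 − 12 = 6. A fully adherent subject scores (18 − 6)/12 = 100%.

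**Partial adherence, all leftover tablets returned.**

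| Pattern | SAP derivation (tablets/12) | SAP definition (doses/10) | Difference (points) |
|---|---|---|---|
| Full course | 12/12 = 100% | 10/10 = 100% | 0 |
| One maintenance dose missed | 11/12 = 91.7% | 9/10 = 90% | +1.7 |
| Two maintenance doses missed | 10/12 = 83.3% | 8/10 = 80% | +3.3 |
| Three maintenance doses missed | 9/12 = 75% | 7/10 = 70% | +5 |
| Loading dose missed | 9/12 = 75% | 9/10 = 90% | −15 |

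If a programmer took the first sentence literally and divided the tablet count by 10 planned doses, full adherence would give 12/10 = 120%.

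**Unreturned tablets.** Full course, none of the 6 spares returned: 18/12 = 150%. Non-return can also hide missed doses. A subject who misses six maintenance doses takes 6 tablets and has 12 left; if only 6 come back, the score is (18 − 6)/12 = 100%, against 4/10 = 40% by doses.

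**Extended dosing.** The Time and Events Schedule allows up to 19 maintenance doses, so 3 + 19 = 22 tablets. Protocol 9.1.4 says more drug may then be supplied, so 18 would no longer be the number dispensed. If 18 were kept anyway, the score could not exceed 18/22 = 82%.

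**Per-protocol first-dose rule, read as a calendar day.**

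| Randomized | First dose | Delay | Within 4 h? | Same day? |
|---|---|---|---|---|
| 22:00 | 01:00 | 3 h | yes | no: excluded |
| 08:00 | 20:00 | 12 h | no | yes: kept |

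None of the criteria listed in SAP 2.3 checks the 4 hours. The rule also does not secure its own stated aim, since the dose taken that day need not be the loading dose: Protocol 9.1.3 allows two doses on Day 1.

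**How many subjects.** The documents give no randomization times. As an assumption only: if randomization is spread evenly over 24 hours, the share crossing midnight is the mean delay divided by 24. A mean delay of 0.5 h gives 0.5/24 = 2%, and 4 h gives 4/24 = 17%, or about 2 to 15 of 90. With daytime-only randomization it is about 0.

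**The case against.** The strongest reply on compliance is that SAP 4.1.3 can be read throughout as tablets over tablets. On that reading 12 is correct, full adherence gives 100%, and one or two missed maintenance doses shift the result by only 2 to 3 points. A tablet ratio also tracks drug amount: in Regimen B a missed loading dose leaves 2,250/3,000 mg = 75%, exactly the tablet score. In Regimen C it leaves 4,500/5,500 mg = 82%, slightly closer to 75% than to 90%. Protocol 14.5 requires all containers to be returned, so 150% presupposes that this was not followed, and 82% needs both an extension and a resupply that is ignored. All of this stands as a limit on the size of the problem. It does not remove it, because the SAP's stated definition is in doses and the derivation does not deliver that.

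A reader might infer that the tablet count decides who enters the per-protocol set. The documents do not say so: SAP 2.3 counts missed doses without naming a source and does not refer to 4.1.3. The gap is the unnamed source.

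A reader might also infer that a subject dosed after midnight is plainly compliant. That is not settled either. Protocol 9.1.3 places randomization and the loading dose together under Day 1, while SAP 4.2.3.1 counts Day 1 from first treatment. Such a subject meets the 4-hour limit but not the Day 1 text.

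Finally, Protocol 11 excludes deviations that affect efficacy assessment, and SAP 4.1.5 says the per-protocol definition considers any such deviation. That might catch a late first dose, but SAP 2.3 bases inclusion on its listed criteria, and the 4-hour limit is not among them.

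**Conclusion.** Two separate wording defects hold. First, SAP 4.1.3 mixes units. Compliance is right for full adherence with the spares returned, but departs from the SAP's own definition for partial adherence, from −15 points (loading dose missed) to +5 points (three maintenance doses missed), and it counts unreturned tablets as taken. Second, the first-dose rule in SAP 2.3 does not match the protocol's 4-hour limit and can misclassify subjects in either direction if read as a calendar day.

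It would be too strong to say that reported compliance is wrong in general, or that any efficacy conclusion is at risk. Compliance is only described, the per-protocol set is supportive (Protocol 11 says it may be used for sensitivity analysis), and the primary analysis uses the ITT-i set, which neither rule affects. The number of subjects crossing midnight cannot be known from the documents; the 2% to 17% range rests entirely on the round-the-clock assumption. Severity: minor.

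**What to change.** **SAP 4.1.3.** Compute compliance as the number of doses with a recorded administration date and time (eCRF in hospital, eCOA log at home) over planned doses: 10, or the extended number. Keep the tablet count as a cross-check and as the fallback where the log has gaps, using tablets actually dispensed rather than a fixed 18.

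**SAP 2.3.** Name the same dosing record as the source for the missed-dose criterion. State directly that the loading dose must have been taken. Reconcile the day-of-randomization wording with the 4-hour window in Protocol 6 and 9.1.3 and with the Day 1 text in Protocol 9.1.3, so that per-protocol membership follows the protocol's own timing limit and the after-midnight case has a stated answer.

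**Cost.** SAP wording and minor programming on data already collected, plus a rule for eCOA log gaps. It should be settled before database lock, since per-protocol membership is decided by then.
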